8.3 SUBJECT INSURANCE

Standard NHS Indemnity only will apply for the protocol and study design and clinical negligence.

The Royal	Document No.	Version	Document Date	Author	Page: 24
Wolverhampton NHS Trust	CIP Study No. 2019OPH108	1.6	03 August 2021	[name]	Out of: 60

GEBAUER MEDIZINTECHNIK GmbH providing the devices hold professional liability for the device and its use.

8.4 SUBJECT ENROLMENT

A Screening/Enrolment Log will be maintained to document selected information about candidates who meet or fail to meet the entry criteria. Subjects meeting all eligibility requirements will be eligible to advance in the study, and they will be assigned a 3 digit Subject Identification Number. If the subject does not meet all of the eligibility requirements, the subject's participation is denied.

All subjects who meet the eligibility requirements will be invited to participate. Subjects will be considered enrolled into the study after:

- 1. A signed Informed Consent has been obtained.
- 2. The subject has met all of the inclusion and none of the exclusion criteria.
- 3. The screening assessments results have been approved by the Chief Investigator

8.5 **PROCEDURAL INFORMATION**

There will be one screening visit followed by the surgical flap creation visit, then the implantation visit and 4 compulsory follow-up study visits. In addition 2 weekly, telephone assessments will be conducted up to 3 months. In addition to that, 2 optional long-term follow-up visits are planned, 1 and 2 years after implantation.

8.5.1 BASELINE EVALUATION (DAY - 30 TO DAY -1)

The pre-procedure data can be collected from 30 days to 1 day prior to the surgical procedure. Obtaining Informed Consent Form is mandatory before any study related procedure is performed. The visit will include subject's eligibility assessment for inclusion and exclusion criteria as described in Section 7. Ophthalmic medical history will be taken including subject's ophthalmic complaints and medications use.

The following examinations will also be performed for both eyes:

- Intraocular pressure (IOP) measurement
- Best corrected visual acuity
- Corneal transparency (slit lamp)
- Photodocumentation of corneal status
- Inflammation of cornea or sclera
- Central corneal thickness measurement (OCT)

The Royal	Document No.	Version	Document Date	Author	Page: 25
Wolverhampton NHS Trust	CIP Study No. 2019OPH108	1.6	03 August 2021	[name]	Out of: 60

- Corneal topography (K-reading map)
- Assessment of corneal epithelium
- Assessment of conjunctiva
- Assessment of iris / pupil
- Assessment of lens
- Assessment of ocular pain
- Assessment of patient satisfaction with treatments and outcome

8.5.2 Day 0 Surgery - Flap Creation

For eligible subjects the Flap creation surgery will be scheduled according to clinical discretion of the responsible ophthalmic surgeon, and in compliance with the provisions described in this Clinical Investigation Plan. The main steps are listed here

• Under topical anesthesia, a mid-stromal pocket will be created using either a femtosecond laser dissection technique or a manual technique. In patients suffering from post-LASIK ectasia, manual techniques will be applied to re-open the pre-existing LASIK flap in the form of a pocket.

8.5.3 Day 0 (+ 30 days) Surgery - Implantaion

For eligible subjects the Implantation of the Gebauer[™] Lenticule surgery will be scheduled according to clinical discretion of the responsible ophthalmic surgeon up to 30 days after the flap creation, and in compliance with the provisions described in this Clinical Investigation Plan. The main steps are listed here

- Under topical anesthesia, the corneal vertex will be marked with gentian violet using the first Purkinje image as a reference while asking the patient to fixate on the microscope light.
- The Gebauer™ Lenticule implant is then gently inserted and fully expanded with no wrinkles into the pocket through the pocket opening.
- The implant is then centered with the corneal vertex.
- Immediately post implantation, essential surgical data will be recorded including procedural details (start and end time), orientation, dimensions and closure method of pocket, use of bandage contact lens, device ease of use, procedure complications and medications prescribed.

The subject will be discharged after the procedure or will be hospitalized for one day according to physician discretion.

The Royal	Document No.	Version Document Date		Author	Page: 26
Wolverhampton NHS Trust	CIP Study No. 2019OPH108	1.6	03 August 2021	[name]	Out of: 60

Post- operatively, antibiotic eye drops will be prescribed for 2 weeks, and steroid eye drops (e.g. PredForte; Allergan) will be prescribed 2 hourly for 2 weeks, along with optional lubricating drops.

Safety Monitoring will be performed (recording of adverse events and medications)

The Royal	Document No.	Version	Document Date	Author	Page: 27
Wolverhampton NHS Trust	CIP Study No. 2019OPH108	1.6	03 August 2021	[name]	Out of: 60

8.5.4 Follow-up Study Visits Post-surgery

Subjects will be followed up frequently for a period of 6 months with ophthalmic assessments at day 1-3; 28 days (+/-7days), 3 months (+/-14 days), 6 months (+/-28 days). In addition to that, patients will be invited to come back to the hospital for two optional long-term follow-up visits 1 and 2 years post implantation. The results of these long-term follow-up visits will be reported separately in an addendum report, independently from the basic follow-up period of 6 months.

Post surgical assessments performed at each follow-up visit will be as follows:

It is recommended to perform all the ophthalmic examination on the same hour \pm 3 hours along the day in all the follow-up visits.

At each follow-up visit, the clinical investigator will perform a detailed ophthalmic examination on the treated and the untreated eye which includes the following:

- Intraocular pressure (IOP) measurement
- Best corrected visual acuity
- Corneal transparency (slit lamp)
- Lenticule transparency (slit lamp)
- Photodocumentation of corneal status
- Inflammation of cornea or sclera
- Signs of immunological rejection
- Central corneal thickness measurement (OCT)
- Corneal topography (K-reading map)
- Assessment of corneal epithelium
- Assessment of conjunctiva
- Assessment of Iris / Pupil
- Assessment of Lens
- Assessment of ocular pain
- Assessment of patient satisfaction with treatments and outcome

In addition to that, safety Monitoring will be performed (recording of adverse events and medications).

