5.2.3 PRIMARY ENDPOINTS FOR EFFECTIVENESS

The following primary endpoints for effectiveness have been determined and will be systematically documented in the Case Report Form for each patient visit:

- Changes in corneal topography (central K-reading results): at baseline vs. post implantation observation period
- Changes in central corneal thickness at baseline vs. post implantation corneal thickness (cornea plus lenticule)
- Patient satisfaction with received treatments and outcome

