For this clinical investigation, the following time frame is anticipated: Completion of active enrolment is expected to require approximately 1-3 months. The primary endpoints will be achieved when the last study subject has completed his/her 6 months follow-up. For the assessment of long-term tolerability, subjects will be invited to additional follow-up visits after 1 and 2 years. Therefore, the total duration of the study is expected to be 9 months (for completion of the 6 months follow-up period), respectively, 27 months (for completion of the 2 years follow-up period).

The Royal	Document No.	Version	Document Date	Author	Page: 22
Wolverhampton NHS Trust	CIP Study No. 2019OPH108	1.6	03 August 2021	[name]	Out of: 60

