8. STUDY PROCEDURES

8.1 SUBJECT SCREENING

Subjects will be selected from the physician's usual patients practice. All subjects meeting the inclusion/exclusion criteria and having signed the Informed Consent Form will be evaluated by the Investigator according to the study protocol.

Any pre-procedure assessment or tests that are required before entering subjects to the study (history and ophthalmic examinations, laboratory tests) will be analyzed and interpreted at the study site.

A screening log will be maintained by the site for all the subjects screened. This list includes both enrolled and non-enrolled patients.

Every effort will be made to correctly establish eligibility of the participants prior to enrolment. Subjects who do not meet all inclusion/exclusion criteria as listed in Chapter 7.1 and 7.2 will not be enrolled in the study.

Where the participant's first language is not English, the Site's interpreting services will be utilised as per Site's standard protocols.

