8.5.5 FOLLOW UP TELEPHONE ASSESSMENTS

Subjects will have 2 weekly telephone assessments up to 3 months post surgery.

The Royal	Document No.	Version	Document Date	Author	Page: 28
Wolverhampton NHS Trust	CIP Study No. 2019OPH108	1.6	03 August 2021	[name]	Out of: 60

The assessments performed at each telephone follow-up will be as follows:

- Assessment of ocular pain
- Assessment of patient satisfaction with treatments and outcome
- Recording of adverse events
- Recording of medications

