13.4 BLINDING

This is an open label study. No blinding of patients and/or investigators is intended.

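### Patient satisfaction (a primary effectiveness endpoint) and ocular pain are collected within the investigator's examination in an unblinded single-arm trial, with no self-completion or independent collector stated, so both may lean favourable

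*Protocol*

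**What the plan says.** Section 5.2.3 of the protocol lists three primary effectiveness endpoints. The third is "Patient satisfaction with received treatments and outcome". Section 5.2.2 lists ocular pain or discomfort among the secondary safety endpoints.

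Section 8.5.4 states that at each follow-up visit "the clinical investigator will perform a detailed ophthalmic examination on the treated and the untreated eye which includes the following". The list runs from intraocular pressure through acuity, slit lamp, OCT and topography. Its last two items are ocular pain and "Assessment of patient satisfaction with treatments and outcome". The synopsis carries the same follow-up list, with both items printed twice. Section 8.5.1 puts both items in the baseline examination list without naming who performs it.

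There is a second route. Section 8.5.5 says "Subjects will have 2 weekly telephone assessments up to 3 months post surgery", and satisfaction and pain are assessed on each call. The caller is not named.

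On the setting, section 13.4 says "No blinding of patients and/or investigators is intended", section 8.1 says "Subjects will be selected from the physician's usual patients practice", and section 6 says "The primary endpoints will be achieved when the last study subject has completed his/her 6 months follow-up".

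**The concern.** Satisfaction and pain are the patient's own reports. If they are collected within the examination by someone the patient associates with the treatment, some patients may answer more kindly than they otherwise would. Recruitment from the physician's own practice makes an existing care relationship likely.

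In a randomised trial such a tendency would fall on both arms and partly cancel. Here there is no second arm. The untreated eye, which section 6 uses as the reference, cannot help, because satisfaction with treatment is rated once per patient and not once per eye.

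At stake are one of the three primary effectiveness results, which could look better than patients' unprompted view, and a safety outcome, which could look milder. Lack of blinding is hard to avoid in a single-arm implant study. Who collects the rating, and when, is easy to change.

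**Working it through.** The protocol gives no rate, standard deviation or success criterion for satisfaction, so there is no planned figure to reproduce. The check is mainly one of reading, followed by an illustration of scale.

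**1. Who collects the ratings, and is there a safeguard?**
- Follow-up visits: both items are in the list performed by the clinical investigator (8.5.4, synopsis).
- Baseline: both items are in the examination list, performer not named (8.5.1).
- Calls: both items are assessed, caller not named (8.5.5).
- Methods: section 11 covers pressure, acuity, slit lamp, OCT and topography. It has no entry for satisfaction or pain.
- Source: section 20 asks that study variables be entered directly in the case report form whenever possible, so no separate patient-completed record is required.

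No section states self-completion or a collector outside the treating team.

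**2. Which ratings are exposed?** Visits up to 6 months fall on day 1–3, day 28, month 3 and month 6, which is 4. Calls fall on days 14, 42, 56, 70 and 84 (8.5.9), which is 5. So 5 of 4 + 5 = 9 scheduled post-implant ratings lie outside the eye examination. The last call is at day 84, so the rating at the 6-month primary time point comes from an in-person visit.

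**3. Does the baseline rating cancel the bias?** Write each observed rating as the true rating plus a courtesy term:

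observed change = true change + (c_post − c_base)

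Only a constant courtesy term cancels. The baseline rating precedes the operation, so it cannot carry courtesy that arises from having been operated on. The offset is partial at best.

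**4. Scale, under assumptions.** Suppose satisfaction is reported as yes/no in n = 15 (section 13.3 gives the 15; the yes/no split is assumed). Exact 95% limits for x satisfied are the 2.5% point of Beta(x, n − x + 1) and the 97.5% point of Beta(x + 1, n − x). Suppose two patients move to satisfied, a rise of 2/15 = 13.3 points:

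| Without shift | 95% CI | With shift | 95% CI |
|---|---|---|---|
| 8/15 (53%) | 27–79% | 10/15 (67%) | 38–88% |
| 10/15 (67%) | 38–88% | 12/15 (80%) | 52–96% |
| 12/15 (80%) | 52–96% | 14/15 (93%) | 68–100% |

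One patient would be 1/15 = 6.7 points and three would be 3/15 = 20 points.

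The probability that the exact interval still contains the true rate p, when answers follow p plus a shift b, is the Binomial(15, p + b) probability of all x whose interval contains p:

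| True rate | b = 0 | b = 5 points | b = 10 points | b = 20 points |
|---|---|---|---|---|
| 50% | 96.5% | 95.1% | 90.8% | 70.3% |
| 60% | 98.5% | 98.3% | 96.4% | 83.3% |
| 70% | 98.0% | 98.2% | 96.4% | 79.4% |

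A shift of 5 to 10 points is largely hidden within the sampling error of 15 patients. A shift of 20 points is not, and the reported interval would give no sign of it.

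**The case against.** The strongest reply is that the text does not fix the mode of collection. Section 8.5.4 names an assessment without saying how it is done. A self-completed form handed out at the visit would fit. Section 16.1 refers to standardized case report forms and section 23 to an ophthalmic examination questionnaire, and neither is shown. That stands, and it is why this is a risk and not a demonstrated error. It does not remove the point, because the only collection route the protocol states is the investigator's examination.

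A reader might infer that the operating surgeon questions the patient face to face at the end of the visit, and that courtesy therefore inflates the result. The documents do not support this. Sections 8.5.2 and 8.5.3 speak of the responsible surgeon and 8.5.4 of the clinical investigator, and they are not said to be the same person. The order of a bulleted list is not a sequence in time. No figure for inflation appears anywhere.

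The telephone ratings and the baseline rating also count in the plan's favour. They narrow the exposure but do not reach the 6-month rating or cancel courtesy that arises after surgery.

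Finally, this is a mainly descriptive feasibility study of 15 patients, and section 13.7.4 names corneal clarity, not satisfaction, as the third primary effectiveness endpoint. That is a separate contradiction. Section 13.2 refers to Chapter 5 for the endpoints, so satisfaction keeps its primary status until the two are reconciled.

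**Conclusion.** The concern holds as a risk. A primary effectiveness endpoint and a secondary safety endpoint, both reported by the patient, are placed within the investigator's examination in an unblinded single-arm trial, with no self-completion or independent collection stated. The 6-month ratings are included. The likely direction is towards favourable answers. The size cannot be derived from the documents.

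The 13-point rise is an illustration resting on an assumed yes/no analysis, assumed starting counts and an assumed two-patient shift. A reader might attach meaning to the lower limit passing 50% when 10/15 becomes 12/15. The protocol sets no such criterion, and the two intervals overlap heavily. What the arithmetic does show is that with 15 patients a few answers change how the result reads.

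The change is worth making because it is cheap and must be in place before the ratings are taken. It does not call the study design into question.

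**What to change.** - In 8.5.1, 8.5.4 and the matching synopsis lists, take satisfaction and ocular pain out of the examination list (and remove the repeated items in the synopsis). State instead that the patient completes both alone, on arrival, before any examination or discussion of results, and hands the form to study staff not involved in the operation. Allow large print, or reading help from non-operating staff, where vision requires it.
- In 8.5.5, state that calls are made by study staff other than the operating surgeon, with the same questions and response scale as at visits, and that the mode of collection is recorded for each rating.
- State that the 6-month result rests on the self-completed visit ratings.

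The cost is a sentence or two in each section and a few minutes per visit. Sections 16.2 and 19.5 already refer to study staff and a delegated research team; that some of them take no part in the operation is an assumption to confirm. The remaining downside is that visit ratings would be written and call ratings spoken, so the two should not be read as one uniform series.

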8.5.5 FOLLOW UP TELEPHONE ASSESSMENTS

Subjects will have 2 weekly telephone assessments up to 3 months post surgery.

The Royal	Document No.	Version	Document Date	Author	Page: 28
Wolverhampton NHS Trust	CIP Study No. 2019OPH108	1.6	03 August 2021	[name]	Out of: 60

The assessments performed at each telephone follow-up will be as follows:

- Assessment of ocular pain
- Assessment of patient satisfaction with treatments and outcome
- Recording of adverse events
- Recording of medications

8.5.6 PROCEDURAL FAILURES

Failure to perform the procedure with the Gebauer[™] Lenticule will be recorded on the CRF as an operative failure. In the event of operative failure to treat or if the surgery had to be terminated unsuccessfully for whatever reasons, a detailed explanation of the circumstances will be recorded and an adverse event form will be filed. The patient will be followed until final decision.

It shall be noted that the Investigator must return any damaged or unused study devices within 24 hours post surgery to the manufacturer of the product, GEBAUER MEDIZINTECHNIK GmbH, [name].

8.5.7 DOCUMENTATION OF THE SURGICAL PROCEDURES

The following data will be recorded during or immediately after performing the procedure:

- Date of procedure, start and end time
- Gebauer[™] Lenticule Identification (Product Number/Batch number)
- IOP of treated eye before surgery
- Method of corneal pocket formation
- Suitability of pocket size
- Orientation / opening of pocket
- Potential suturing after implantation
- Potential use of bandage contact lens
- Antibiotic and immunosuppressive treatments
- Overall implantation success
- Investigator's overall procedure evaluation
- Date of discharge from hospital post surgery
- Any procedural adverse events

All relevant information is recorded in the CRF's.

The Roval	Document No.	Version	Document Date	Author	Page: 29
Wolverhampton NHS Trust	CIP Study No. 2019OPH108	1.6	03 August 2021	[name]	Out of: 60

8.5.8 POST IMPLANTATION MEDICAL TREATMENTS

Post- operatively, antibiotic eye drops will be prescribed for 2 weeks, and steroid eye drops (e.g., PredForte; Allergan) will be prescribed 2 hourly for 2 weeks (along with optional lubricating drops), and subsequently in tapering doses. All treatment-related medication will be documented in the Concomitant Medications Form.

The Royal	Document No.	Version	Document Date	Author	Page: 30
Wolverhampton NHS Trust	CIP Study No. 2019OPH108	1.6	03 August 2021	[name]	Out of: 60

8.5.9 SUMMARY SCHEDULE OF VISITS AND PROCEDURES

In the below Table, a summary of all planned patient visits and related procedures is provided:

Assessment Procedure	Baseline (-30 – 1 d)	Flap cre- ation (0d)	Implanta- tion (0 ± 30 d)	Follow- up 1 (1 – 3 d)	Tele- phone Follow- up 1 (14 ± 2 d)	Follow- up 2 (28 ± 7 d)	Tele- phone Follow- up 2 (42 ± 2 d)	Tele- phone Follow- up 3 (56 ± 2 d)	Tele- phone Follow- up 4 (70 ± 2 d)	Tele- phone Follow- up 5 (84 ± 2 d)	Follow- up 3 (3 M ± 14 d)	Follow- up 4 (6 M ± 28 d)	Long Term Fol- low-ups (1, 2 y etc.)
Informed Con- sent	x												
Inclusion & Ex- clusion Criteria	x												
Ophthalmic medical history	x												
Intraocular pres- sure (IOP) measurement	X	x	x	x		x					x	x	x
Best corrected visual acuity	X			x		x					x	x	x
Corneal trans- parency (slit lamp)	X			x		x					x	x	x
Lenticule trans- parency (slit lamp)				x		x					x	x	x

	The	Royal	Docume	ent No.	Version	Documen	t Date	Au	thor	Page	e: 31		
	Wolver	hampton 5 Trust	CIP Stu 2019Ol		1.6	03 Aug 202		[name]	Out o	of: 60		
Photodocum tation of corr status		x			x	x					x	x	x
Inflammation cornea or scl		x		2	x	x					x	x	x
Signs of munolog cal rejec	ji-				x	x					x	x	x
Central corr thickness me urement (OC	eas-	x			x	x					x	x	x
Corneal top raphy (K-re ing map)		x			x	x					x	x	x
Assessment corneal epit lium		x			x	x					x	x	x
Assessment conjunctiva	of	x			x	x					x	x	x
Assessment iris / pupil	of	x			x	x					x	x	x
Assessment lens	of	x			x	x					x	x	x
Assessment ocular pain	of	x			x x	x	x	x	x	x	x	x	x
Assessment patient satist tion with tro ments and o come	fac- eat-	x			x	x	x	x	x	x	x	x	x

	The	Royal	Document N	lo. Ve	rsion	Document	Date	Aut	thor	Page	e: 32		
	Wolverh	nampton Trust	CIP Study N 2019OPH1	lo. 08	1.6	03 Augu 2021	ust	[name]	ango	Out c	of: 60		
Request for of tom-made vice for par pant	de-	2											
Device Impl tation	lan-		x										
	eye ore-		x										
drops p	eye ore- ong lu- os.		x										
Flap creation		x	 										
Lenticule plantation CRF	lm- &	×	x										
Ophthalmic amination CF	Ex- RF X	x	x	X		x					x	x	x
Documentation of Concomit Medication (Ophthalmic General)	tant X	x	x	x	x	x	X	x	x	X	x	x	x
Documentation of AE / SAE	on x	x	x	x	x	x	X	x	x	X	x	x	x

The Royal	Document No.	Version	Document Date	Author	Page: 33
Wolverhampton NHS Trust	CIP Study No. 2019OPH108	1.6	03 August 2021	[name]	Out of: 60

The Roval	Document No.	Version	Document Date	Author	Page: 34
Wolverhampton NHS Trust	CIP Study No. 2019OPH108	1.6	03 August 2021	[name]	Out of: 60

9. INDICATIONS FOR DEVICE REMOVAL

The Gebauer™ Lenticule should be removed from the subject's eye in the following circumstances:

- Uncontrolled cornea erosion
- Cornea melting
- Cornea perforation
- Severe infection (contamination of Implant)
- In case the cornea becomes thinner than 75% of its normal thickness a close follow-up should be performed. When cornea becomes less than 50% of its normal thickness the Gebauer™ Lenticule should be removed.
- Inflammatory processes as red eye
- Peripheral neo-vascularization
- Other symptoms of activation of immunological pathways
- Any condition in the discretion of the PI that may be resulting from the implantation of Gebauer[™] Lenticule and deemed to have a long term effect on the eye.

